7.7. Statistical Modifications

Modifications to the statistical section of the protocol are listed as follows.

- The protocol states “The FAS will include all participants who are randomized and took at least one dose of study medication. Participants are analyzed according to randomized treatment.” We have observed serious deviations and significant breaches to the principles of Good Clinical Practice during the study at Site 1865, especially in the collection of efficacy data. These deviations and breaches are suspected to be gross misconduct and thus considered to have compromised the integrity of the efficacy data collected and reported by this site. This SAP thus defines Full Analysis Set 1 and Full Analysis Set 2 to accommodate the exclusion of Site 1865 from efficacy analyses.
- The protocol states that “The mFAS population will include all participants who are randomized, took at least one dose of study medication, and have baseline and any post-baseline assessment of CAPS-5 total score, CGI-S, or PGI-S score, excluding ineligible participants that were randomized”. This SAP defines the Modified Full Analysis Set as “includes all participants in the Full Analysis Set 1 who have baseline and at least 1 post-baseline assessment of CAPS-5 total score, CGI-S, or PGI-S score, excluding ineligible participants that were randomized” to accommodate the exclusion of Site 1865 from the supplementary efficacy analyses using mFAS.
- The protocol states “the mFAS analysis set will be the primary analysis set for all efficacy analyses.” At FDA’s recommendation to use FAS, this SAP defines the main

Jazz Pharmaceuticals
 {Statistical Analysis Plan - Protocol #}JZP150-201-02

efficacy analysis set as “The Full Analysis Set 1 which includes all participants who were randomized and took at least 1 dose of the study intervention, excluding Site 1865.” This analysis set will be the primary analysis set for all efficacy analyses.

- The protocol states that time-dependent multiple imputation will be included as a sensitivity analysis. Due to limited collection of post-ICE efficacy follow up data, the time-dependent multiple imputation will not produce robust estimates and therefore will not be included in this SAP.
- The protocol states that the 2-dimentional tipping point analysis will be included as a sensitivity analysis. This SAP will use the traditional 1-dimentional tipping point analysis to include more details in the results display, such as LS means, LS mean differences, SE, and 95% CI, that are associated with different deltas (shifts).
- The protocol states that “The PK Analysis Set will include all participants who receive at least 1 dose of study intervention and have at least 1 pre-dose or 1 post-dose evaluable PK concentration.” This SAP has been modified to “The PK Analysis Set will include all participants who receive at least 1 dose of study intervention and have at least 1 post-dose (post first dose) evaluable PK concentration.”

8. STUDY POPULATION SUMMARIES

8.1. Enrollment

The total number and percentage of participants for each Analysis Set defined in [Section 6](#) will be summarized overall and by randomized treatment group.

8.2. Participant Disposition

All participants who provide signed ICF will be accounted for in this study. The number and percentages of screen failure participants will be presented by overall among the Enrolled Analysis Set. The number and percentages of participants who received at least one dose, completed, discontinued early from study intervention, and discontinued early from study, including reasons for early discontinuation, will be presented overall and by randomized treatment group among the Enrolled Analysis Set and Full Analysis Set 2. The number and percentage of participants by study site/Investigator will also be summarized among the Enrolled Analysis Set and Full Analysis Set 2.

A concordance analysis using Cohen’s kappa will be conducted using the Full Analysis Set 1 to examine the agreement of the classification of participants into randomization strata using different data sources, i.e., the IRT vs the electronic data capture (EDC). In case of discrepancies between IRT and EDC, the randomization stratum recorded in IRT will be used in efficacy analyses and the randomization stratum recorded in EDC will be used in safety analyses.

The following provides the example SAS code for the Cohen’s kappa analysis:

```
PROC FREQ;
  TABLE IRT*EDC / AGREE;
  RUN;
```

Jazz Pharmaceuticals
 {Statistical Analysis Plan - Protocol #}JZP150-201-02

A participant is considered to have completed the study intervention if he/she has completed the double-blinded treatment period, including receipt of 12 weeks of study intervention. A participant is considered to have completed the study if he/she has completed all periods of the study including the last scheduled procedure in the safety follow-up visit. The participants who discontinue the study intervention early but remain in the study are not considered study completers.

Note that the participant disposition listing will capture the reason for withdrawal including any participant who discontinues from the study due to acquisition of COVID-19 (or other) pandemic.

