9.4.6. Other Analyses

Subgroup analyses for the efficacy and safety assessments will be provided by baseline presence or absence of concomitant use of SSRIs/SNRIs. Subgroup analyses by gender or other

characteristics as defined in the SAP will be provided for efficacy and safety assessments as appropriate.

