7.5. Subgroups and Subgroup Analyses

Subgroup analyses will be conducted on the primary and key secondary efficacy endpoints for the following:

- Randomization stratum: presence vs absence of concomitant use of SSRIs/SNRIs
- Age group 1 (years): ≤ 65 vs > 65
- Age group 2 (years): ≤ 45 vs > 45
- Gender (male vs female)
- Race (white vs black vs other)
- Ethnicity (Hispanic or Latino vs Not Hispanic or Latino)
- High enrolling sites (≥ 20 randomized participants) (high enrolling sites combined vs all other sites combined)

Should there be less than 20 participants in any subgroup, then only summary statistics will be presented.

The output for estimating the treatment difference within subgroup will not be provided (least square [LS] means, standard error [SE], LS Mean Difference (95% confidence interval [CI]) or median difference (95% CI) and p-value) if the data are too sparse.

It should be noted that the study was not designed to detect treatment differences with high statistical power within any subgroups.

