8.6. Protocol Deviations

Protocol deviations as classified in the Clinical Trial Management System (CTMS) will be summarized using the Full Analysis Set 2 by type of deviation and severity (important or non-important). All protocol deviations will also be provided in a data listing.

Jazz Pharmaceuticals
{Statistical Analysis Plan - Protocol #}JZP150-201-02

If changes to study conduct occur due to COVID-19 restrictions, they will be reported as protocol deviations. These deviations will be summarized separately by the classification type in CTMS and included in a data listing.

Discrepancies between IRT and EDC (i.e., wrong randomization stratum recorded in IRT) will be reported as protocol deviations. The approach to address these discrepancies is described in [Section 8.2](#) and [Section 9.1.3.4](#).

Dosing in error will be reported as protocol deviations. The mis-dosed participants will be summarized by their randomized treatment arm in efficacy analyses. For safety analyses, the mis-dosed participants will be summarized by their treatment arm determined by the first actual dose.

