9.1.3.4. Additional Sensitivity Analyses

Additional sensitivity analyses may be performed by using the randomization stratum recorded in EDC in case of discrepancies between IRT and EDC.

Jazz Pharmaceuticals
 {Statistical Analysis Plan - Protocol #}JZP150-201-02

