9.1.4. Subgroup Analyses

Subgroup analyses for groups specified in [Section 7.5](#) will be performed for the primary efficacy estimand using the Full Analysis Set 1, for each of the prespecified subgroups. Subgroup variable by treatment interaction will be estimated for Week 12. Normality assumptions will not be reassessed for subgroups. The corresponding parametric or nonparametric analysis used for the overall sample will be applied to each subgroup. Numeric results for subgroup analyses will be summarized. A forest plot summarizing the treatment difference, 95% CI, and p-value for the interaction term estimated at Week 12 will also be provided by each subgroup.

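### If IRT and EDC disagree on SSRI/SNRI use, the SAP forms the efficacy subgroups from the IRT entry that it calls wrong, while the protocol defines them by baseline use

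*SAP*

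**What the plan says.** SAP 7.5 lists the subgroup as "Randomization stratum: presence vs absence of concomitant use of SSRIs/SNRIs". SAP 9.1.4 makes it an efficacy analysis: the subgroup analyses "will be performed for the primary efficacy estimand using the Full Analysis Set 1, for each of the prespecified subgroups", with a forest plot and an interaction p-value at Week 12. SAP 9.2.4 does the same for CGI-S and PGI-S.

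SAP 8.2 settles disagreements between the two sources by type of analysis. For efficacy, "In case of discrepancies between IRT and EDC, the randomization stratum recorded in IRT will be used in efficacy analyses"; for safety, "the randomization stratum recorded in EDC will be used in safety analyses". Subgroups are not excepted. SAP 8.6 says which source it regards as mistaken: "Discrepancies between IRT and EDC (i.e., wrong randomization stratum recorded in IRT) will be reported as protocol deviations".

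Protocol 9.4.6 words the subgroup as a participant characteristic, "by baseline presence or absence of concomitant use of SSRIs/SNRIs", with one definition for efficacy and safety. Protocol 4.2 links the stratified enrolment to assessing users and non-users. SAP 7.7, which lists departures from the protocol's statistical section, does not mention this one.

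**The concern.** Adjusting for the stratum and forming a subgroup serve different purposes. The model covariate should reflect how participants were randomized, so the IRT entry is the right choice there even when it was mis-keyed. The subgroup asks whether JZP150 works differently in people who are or are not taking an antidepressant, and that depends on what they were actually taking. Under the SAP's rule, a participant on an SSRI who was entered as absent in IRT would appear as a non-user in the forest plot.

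Two things are at stake if discrepancies occur. The estimated difference in effect between users and non-users would be pulled toward zero. Also, efficacy and safety results under the same subgroup label would not describe exactly the same participants. The second matters to the extent that the safety subgroup promised in Protocol 9.4.6 is produced, because SAP section 10 does not itself set out a safety table by stratum.

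**Working it through.** The plan gives no figure on this point, so the first step is a comparison of texts and the second is an illustration under stated assumptions.

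**Step 1. The rules side by side**

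| Question | Protocol 9.4.6 | SAP |
|---|---|---|
| What defines the efficacy subgroup? | Baseline use | Randomization stratum (7.5) |
| Source if records disagree, efficacy | Not named | IRT (8.2) |
| Source if records disagree, safety | Not named | EDC (8.2) |
| Which record is in error? | Not addressed | IRT (8.6) |

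If IRT and EDC agree for everyone, the two definitions select the same people. They differ only for discrepant participants.

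**Step 2. Dilution**

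Inputs, both assumed: p = true share of users; e = probability that the IRT entry is wrong, equal in both directions. The entry is made at randomization, before allocation, so error is taken as independent of arm.

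- PPV = p(1−e) / [p(1−e) + (1−p)e], the share of labelled users who are users.
- NPV = (1−p)(1−e) / [(1−p)(1−e) + pe], the share of labelled non-users who are non-users.
- Each labelled subgroup's effect is a weighted mean of the two true effects, so expected contrast = (PPV + NPV − 1) × true contrast.

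With p = 0.30:

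| e | Misplaced of 270 | PPV | NPV | Contrast kept | Shrinkage |
|---|---|---|---|---|---|
| 0.02 | 5.4 | 0.294/0.308 = 0.955 | 0.686/0.692 = 0.991 | 0.946 | 5% |
| 0.05 | 13.5 | 0.285/0.320 = 0.891 | 0.665/0.680 = 0.978 | 0.869 | 13% |
| 0.10 | 27 | 0.270/0.340 = 0.794 | 0.630/0.660 = 0.955 | 0.749 | 25% |

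At e = 0.05, the fraction kept is 0.813 with 20% users and 0.900 with 50% users, so shrinkage is 19% and 10%. Over the whole grid (20% to 50% users, 2% to 10% error) the fraction kept runs from 0.665 to 0.960, a shrinkage of 4.0% to 33.5%.

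**Step 3. Size against sampling error**

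Protocol 9.2 gives 75 completers each on placebo and 4 mg and an SD of 10.5. These inputs, with a difference of 6, reproduce the stated power for that comparison: 93.5% by the noncentral t, against 93.4% stated. With 30% users there are 22.5 users and 52.5 non-users per arm, so

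SE of contrast = 10.5 × √(2/22.5 + 2/52.5) = 10.5 × √0.127 = 3.74 points.

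Take an extreme case: a true effect of 6 in non-users and 0 in users, a contrast of 6.

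| e | Expected contrast | Loss | Loss in SEs |
|---|---|---|---|
| 0.02 | 5.68 | 0.32 | 0.09 |
| 0.05 | 5.21 | 0.79 | 0.21 |
| 0.10 | 4.49 | 1.51 | 0.40 |

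By the normal approximation, power for that interaction is about 36% with no error (6/3.74 = 1.60, against 1.96) and about 29% at 5% error.

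**The case against.** The best defence has four parts.

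- **No discrepancy is on record.** SAP 8.2 and 8.6 say what to do if one arises. A reader might infer from the wording of 8.6 that participants have been misclassified. The documents do not show that, so the point stays conditional.
- **Analysing as randomized is correct.** This stands for the main MMRM and the CMH tests, and nothing here argues against it. It does not carry over to the subgroup. Baseline use precedes treatment, so comparisons within subgroups formed on actual use are still randomized comparisons.
- **The SAP already has safeguards.** It plans a kappa analysis in Full Analysis Set 1, reports discrepancies as protocol deviations and tabulates baseline SSRI/SNRI use. These would disclose a material error rate but would not move anyone to the right subgroup. SAP 9.1.3.4 says "Additional sensitivity analyses may be performed by using the randomization stratum recorded in EDC in case of discrepancies between IRT and EDC"; this is optional and does not name the subgroups.
- **The subgroup is underpowered and descriptive.** SAP 7.5 says so, and the figures above agree. This limits how much the point matters.

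The two definitions are also close in wording, since SAP 7.5 labels the stratum by presence or absence of use, and Protocol 9.4.6 names no data source. The conflict therefore arises only through the tie-break rule in 8.2.

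**Conclusion.** The point holds as a conditional and minor one. If IRT and EDC disagree, the SAP places participants in the SSRI/SNRI efficacy subgroup by the record it regards as wrong. This departs from Protocol 9.4.6 and from the SAP's own choice for safety, and it is not listed in SAP 7.7. With 30% users and a symmetric, arm-independent error of 2%, 5% or 10%, the contrast shrinks by about 5%, 13% or 25%. Even with an assumed true contrast of 6 points, that is at most 0.40 of a standard error. The error rate, its symmetry and the share of users are all assumptions.

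Two stronger readings are not supported. A reader might infer that the trial's main conclusions are at risk, but the primary and key secondary tests rightly use the IRT stratum and do not depend on the subgroup definition. A reader might also infer that the protocol intends this contrast to set the population of later studies. Protocol 1.1 and 2.1 say that of the study's results as a whole and do not mention antidepressant use there; Protocol 4.2 says only that users and non-users can both be assessed.

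**What to change.** - Keep the IRT stratum as covariate in the main MMRM analyses and as stratification factor in the CMH analyses.
- In SAP 7.5 and 8.2, define the SSRI/SNRI efficacy subgroup for the primary and key secondary endpoints by baseline use recorded in EDC, in line with Protocol 9.4.6. Name the variable: randomization is stratified on stable use at Screening, and the documents do not establish that the EDC stratum in the kappa analysis is the same item as the baseline use tabulated under SAP 8.3.
- In the models for this subgroup, omit the IRT stratum and stratum-by-week terms. With IRT-defined subgroups they are constant within each subgroup. With EDC-defined subgroups they would be estimated only from the few discrepant participants and be nearly collinear with the subgroup.
- If any discrepancies occur, show the IRT-based subgroup result as a sensitivity analysis.
- Add the definition to SAP 7.7 if the IRT rule is kept instead.

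The cost is a few sentences and one subgroup flag. Baseline use is already planned for tabulation, so no new data are needed and the main analysis does not change. If the sources agree throughout, the subgroups will be identical.

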8.3. Demographic and Baseline Characteristics

Demographics and baseline data will be summarized by randomized treatment group and overall for the Full Analysis Set 1, PK, and PD Analysis Sets and by treatment group and overall for the Safety Analysis Set. The denominators for calculating the percentages of categorical variables will be the number of participants in each analysis set.

Demographics and baseline characteristics to be summarized include:

- The age derived from date of birth and informed consent date will be used.
- Age groups as defined in [Section 7.5](#)
- Gender
- Race. Participants who reported more than one race will be reported under ‘multiple’ race category.
- Ethnicity
- Height (cm), weight (kg), and body mass index (BMI) (kg/m^2) at Baseline
- Childbearing potential
- Presence of concomitant use of SSRIs/SNRIs at Baseline

Other baseline characteristics such as MINI, C-SSRS (baseline/screening version), LEC-5, and medication washout during Screening will be listed. C-SSRS and LEC-5 will be summarized.

8.4. Medical History

Medical/surgical history are defined as those medical/surgical conditions which started prior to study intervention. The medical/surgical history data will be summarized by treatment group and overall for the Safety Analysis Set and by randomized treatment group and overall for the Full Analysis Set 2.

Medical/surgical history reported terms will be coded to a System Organ Class (SOC) and Preferred Term (PT) using the most recent version of the Medical Dictionary for Regulatory Activities (MedDRA) dictionary version (24.0 or later). Participants’ Medical/surgical history data (other than PTSD) by SOC and PT for each of the analysis sets will be summarized. A participant with multiple medical conditions will be counted once per SOC and PT. The summary table will be sorted by descending order of frequency of SOC in the JZP150 4 mg

Jazz Pharmaceuticals
 {Statistical Analysis Plan - Protocol #}JZP150-201-02

treatment arm (then alphabetically for ties), then by descending order of frequency of PT within each SOC (then alphabetically for ties).

The PTSD disease history will be summarized for the Safety Analysis Set and the Full Analysis Set 1. Key disease history variables include:

- Time since PTSD symptom onset and initial diagnosis (years) – calculated relative to date of ICF signing (See for handling partial dates)
- Name and status of psychotherapy, if any

Listings will also be provided for medical/surgical history and PTSD disease history.

8.5. Prior and Concomitant Medications

Medications will be coded to the anatomical therapeutic class (ATC) level 4 and preferred drug name using the World Health Organization (WHO) drug dictionary, version GLOBALB03Mar2021 or later, and will be classified as follows (See [Appendix 2](#) for handling of partial dates for medications):

- **Prior medications** are defined as any protocol-specified collection of medications which have an end date before the first dose of study intervention.
- **Concomitant medications** are defined as any medication which started prior to and is ongoing at the time of first dose of study intervention or is started on or after the first dose of study administration up to the last dose of study intervention.
- **Post medications** are defined as any medications which started after the last dose of study intervention.

Medications will be summarized by ATC level 4 and preferred drug name. Additionally, disease-related medications will also be summarized and defined as those medications taken for the treatment of PTSD symptoms.

Summaries will include all prior medication, disease-related prior medications, concomitant medications, and disease-related concomitant medications by overall and treatment group in the Safety Analysis Set.

Disease-related prior and concomitant medications will also be summarized by overall and by randomized treatment groups using the Full Analysis Set 1.

All prior, concomitant, and post medications will be included in a data listing. Post medications will be flagged in the data listing but will not be summarized.

8.6. Protocol Deviations

Protocol deviations as classified in the Clinical Trial Management System (CTMS) will be summarized using the Full Analysis Set 2 by type of deviation and severity (important or non-important). All protocol deviations will also be provided in a data listing.

Jazz Pharmaceuticals
{Statistical Analysis Plan - Protocol #}JZP150-201-02

If changes to study conduct occur due to COVID-19 restrictions, they will be reported as protocol deviations. These deviations will be summarized separately by the classification type in CTMS and included in a data listing.

Discrepancies between IRT and EDC (i.e., wrong randomization stratum recorded in IRT) will be reported as protocol deviations. The approach to address these discrepancies is described in [Section 8.2](#) and [Section 9.1.3.4](#).

Dosing in error will be reported as protocol deviations. The mis-dosed participants will be summarized by their randomized treatment arm in efficacy analyses. For safety analyses, the mis-dosed participants will be summarized by their treatment arm determined by the first actual dose.

9. EFFICACY

Unless otherwise described, efficacy data will be primarily summarized by randomized treatment groups using the Full Analysis Set 1, and treatment comparison will be conducted between the randomized treatment groups versus placebo. Efficacy data will be summarized using descriptive statistics by time point. Data listings will also be presented for all efficacy endpoints. The Modified Full Analysis Set and Full Analysis Set 2 will be used in supplementary analyses for efficacy endpoints.

Efficacy data from Site 1865 was excluded from the primary analysis set Full Analysis Set 1 due to observed serious deviations and significant breaches to the principles of Good Clinical Practice during the study, especially in the collection of efficacy data. These deviations and breaches are suspected to be gross misconduct and thus considered to have compromised the integrity of the efficacy data collected and reported by this site. A supplemental analysis using Full Analysis Set 2 will be conducted which does include this site's efficacy data.

9.1. Primary Efficacy Estimand and Analysis

9.1.1. Primary Estimand

The attributes of the primary estimand are described in [Section 4.2.1](#).

The CAPS-5 is a structured, clinician administered, clinical interview wherein participants report on their symptoms of PTSD ([Weathers et al 2018](#)). The CAPS-5 will be administered by qualified medical personnel (i.e., principal investigator, clinical rater). It is a well-established, widely used, and validated assessment that captures PTSD symptom frequency and intensity over the past week using a 5-point Likert-type rating scale.

The CAPS-5 total score is derived by summing the scores over the 20 items from the 4 PTSD symptom clusters/subscales: intrusive symptoms (items B1, B2, B3, B4, and B5), avoidance symptoms (items C1 and C2), arousal/reactivity symptoms (items E1, E2, E3, E4, E5, and E6), and negative alterations in mood and cognition (items D1, D2, D3, D4, D5, D6, and D7). Each item is rated with a single severity score on a 5-point rating scale (0-4) corresponding to the following categories: 0- Absent, 1- Mild/subthreshold, 2- Moderate/threshold, 3- Severe/markedly elevated, and 4- Extreme/incapacitating. The CAPS-5 total score ranges between 0 and 80. The intrusive symptoms subscale score ranges between 0 and 20; the

Jazz Pharmaceuticals
 {Statistical Analysis Plan - Protocol #}JZP150-201-02

avoidance symptoms subscale score ranges between 0 and 8; the arousal/reactivity symptoms subscale score ranges between 0 and 24; and the negative alterations in mood and cognition subscale score ranges between 0 and 28. Higher scores indicate more severe PTSD symptoms. The CAPS-5 total score is assessed at Baseline and end of Weeks 4 and 12.

